The issue of pre-procedural anxiety is critically important because it not only impacts patient experience and is associated with psychological and physiological distress, but it can affect the efficiency of medical procedures, length of stay in the hospital (LoS), and resource utilization – all of which have economics impacts to both families and the health

system. During medical imaging procedures specifically, anxiety can cause non-compliance or unintentional movement which often leads to failure to complete the procedure or poor image quality, necessitating multiple attempts or the use of sedation to achieve the desired quality of imaging. The impact of sedating a patient has several downstream effects, including the increased potential for adverse events, as well as the need for specialized clinical staff (i.e. Anesthesiologists, Post-Anesthetic Care Nurses, etc.), medications, and lengthier post-procedural monitoring. Studies have also indicated an increase in negative post-procedural outcomes when patients are sedated, such as increased pain perception, increased pharmaceutical consumption, reductions in sleep and eating, generalized anxiety, and greater dissatisfaction.²⁻⁸

Child Life Magnetic Resonance Imaging (MRI) Simulations

The literature suggests that approximately 50-to-75% of all patients who undergo MRI exams at pediatric hospitals are sedated.⁹ CLS reduce sedation rates by exposing pediatric patients to MRI simulations, thus alleviating symptoms of pre-procedural anxiety and distress. MRI simulations include mock scans that appear and sound identical to the real MRI, but lack the magnet, and thus functionality to take images. It's suggested that preparation programs like this can reduce sedation rates by about 20% (those who are eligible, recruited, and successful).⁹

Between November 2017 and January 2019, approximately 377 of the pediatric patients attending BCCH for MRI were eligible and referred for preparation with a CLS. Of the patients who proceeded with simulation (N=344), 82% were able to successfully be converted to a non-sedated MRI (**Table 2**).

Table 2. Simulation statistics from BC Children's Hospital (BCCH) Child Life Department, Nov2017 – Jan2019.

	Non-Sedated MRI	Sedated MRI
Passed Simulator	283	8
Failed Simulator	0	53
TOTAL	283	61

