A minimum of 93 participants (31 participants per group) aged 4-to-13 will be recruited through convenience sampling, consented, and randomized by staff to one-of-three preparation programs (VR, mock MRI, or booklet). Details of the comparison groups are outlined in **Table 4**. Given the restricted availability of the simulator, child life specialists, and the availability of participants, we are unable to fully randomly allocate participants. As such, participants will be randomly assigned to the intervention options available according to their individual availability (using Research Randomizer <https://www.randomizer.org/>). For example, if a participant is available on a Thursday that virtual reality and booklet are available, they will be randomly allocated to one of these interventions.

This phase will have open recruitment to all children and adolescents interested in participating, such that participants may not be BCCH patients scheduled for an MRI. This recruitment strategy was selected due to the resource constraints associated with limiting the evaluation group to MRI patients only.

Table 4. Details of the comparison groups.

	VR Simulation	MRI Preparation Booklet	Mock MRI
Facilitator	Research Assistant	Research Assistant	Child Life Specialist
Location	BCCH	BCCH	Simulation Room
Content	Refer to The Virtual Reality Simulation	Refer to MRI Preparation Book	Individualized intervention in physical simulator.

The different interventions will be held in separate private rooms located in BCCH, such that the VR and booklet groups will not have prior exposure to the imaging centre or the simulation room in advance of their assessment. This is to simulate our intended delivery in hospital, medical office, or clinic settings but minimize alternative explanations associated with testing in the simulation room where assessments will take place (previously described in **Table 3**).

Data will be collected throughout the implementation process (**Figure 3**). The predictive variables (demographics and relevant history, and delivery type) will be captured at the start of the session. The primary outcome variable is likelihood of success (pass/fail) of the MRI simulation, and will be measured at the end of the assessment. Anxiety will also be measured at three time points. Usability testing will be conducted throughout to capture possible quality improvements and amendments to each of the program delivery modes.

Inclusion/Exclusion Criteria

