Participants must be between the ages of 4-to-13 years to be included in the evaluation.

The following exclusion criteria, which have been noted in previous studies conducted using virtual reality programs, will be adopted for this project:

- mental disability (content not appropriate)
- significant visual and auditory impairment (this program focuses on auditory and visual cues)
- inability to speak or understand English (content and study staff are English speaking)
- history of seizures or epilepsy (triggered by virtual reality)
- facial or head wounds (cannot wear the virtual reality headset)

Implementation Plan

[figure not shown]

Figure 3. Implementation process.

The testing phase of the implementation process, depicted in Figure 3 will be completed over two hours, and will involve the following steps:

- 1) Participants and parents/guardians are greeted by staff and enter the intervention room.
- 2) Staff will obtain written consent from parents and verbal assent from children (5 minutes).
- 3) Participants will complete the Venham Picture Test (VPT) with staff (pre-test). In parallel, parents will complete the Short STAI on the iPad. (5 minutes)
- 4) Staff will reveal the allocated delivery mode (VR, mock MRI, or booklet) to the participant and explain the procedure.
- 5) Staff will ask participants to indicate on the Smileyometer how good they think the intervention is going to be.^{30,31} This will give a measure of expectation that can indicate whether or not the participant is subsequently let down by the activity or pleasantly surprised.
- 6) Staff will measure the participant's interpupillary distance using sliding calipers.
- 7) Participants will be given 45 active minutes to engage with the intervention. Groups include:

Group 1 (VR): The VR group will receive a virtual reality simulation designed during Phase 1 of this study.

Group 2 (mock MRI): The mock MRI will be provided by the CLS, according to the current care plan which consists of exposing children to the mock MRI, medical devices, and procedures. The mock MRI is located within the BCCH medical imaging facility.

Group 3 (booklet): The standard MRI preparation booklet group will provide access to a series of printed photos and text showing the MRI experience step-by-step to help prepare for the MRI.

- 8) Participants will be asked to indicate on the Smileyometer how good they actually thought the activity was overall (1 minute).

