- 9) Participants will be informed that they will now be completing a simulation test with the MRI scanner. Participants will be reminded of their free and informed ongoing consent.
- 10) The participant will be transferred to the simulation room, located in the medical imaging center at BCCH. Upon entering the simulation room, participants will verbally complete the VPT with staff (during test). In parallel, parents will complete the Short STAI on the iPad. (5 minutes)
- 11) Participants will be guided through a mock MRI and be assessed using MoTrack®, an objective head motion tracking system.³² The simulation will be completed over 20 minutes and will involve progression through the “MRI procedure”, remaining in the bore for 8 minutes. All participants will receive the same type of simulated scan. We will not be simulating any invasive procedures that can sometimes occur during the MRI (i.e. an IV or intravenous contrast liquid). Please note that this assessment involves a mock procedure using the simulator, not a real MRI.
- 12) Immediately following the simulation, participants will verbally complete the VPT with staff (post-test). In parallel, parents will complete the Short STAI on the iPad. (10 minutes).

- 13) Users will be asked to indicate on the *Smileyometer* how they thought the preparation activity was overall in preparing them for the MRI. Parents/guardians will be asked to complete the USE Questionnaire.
- 14) Staff will ask the user open-ended questions on the preparation materials according to three separate criteria of fun, ease of use, and how good it was for learning about the MRI experience. The final usability assessment will take a total of 10 minutes.
- 15) After the session is "complete", children will be told that they "happen to have some time left" so they can play with any of the preparation materials offered (VR, Mock MRI, Booklet) for 5-minutes if they want to "because they did so well during the activity." This will give children a natural choice selection and will be used to gauge preferences for the activities.
- 16) A verbal session debrief will include an opportunity for questions to mitigate any residual feelings of discomfort or anxiety that may arise from the project's activities.

Outcome Measures

The measures used to evaluate the intended outputs and outcomes associated with this project are outlined below (**Table 4**).

Table 4. Outputs and outcomes associated with the project.

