The predictive success in avoiding sedation will be measured using Motrak® software assessment. MoTrak® uses a sensor attached to the participant's head to determine the position of the head in space relative to a transmitter located within the simulator. The sensor records angular rotations as well as positional displacements from an initially calibrated position. This information is displayed and logged by the program in real-time, allowing objective observation of head motion in an MRI simulator.³² The fail threshold is set at 3mm of movement in any of the positional displacements (x,y,z), which is in accordance with imaging protocols at the Hospital.

Child Anxiety: Venham Picture Test – 5 minutes

Anxiety assessment with children will be completed in pictorial form to better adapt to the cognitive and communicative abilities and styles of younger children. The Venham Picture Test has been well-validated in children for assessing procedural anxiety^{33,34}, and comprises eight cards which two figures on each card, one anxious character and one non-anxious character. The children will be asked to point at the figure they feel most like at that moment. All cards will be shown in their number order. If the child points at the anxious figure, a score of one is recorded and if the child points at the non-anxious character, they will be given a score of zero. Children will complete the at three timepoints (before, during, after the mock MRI).

Secondary Measures

Parental Anxiety: Short State-Trait Anxiety Inventory (Short STAI) – 5 minutes

Anxiety assessment with parents/guardians and children at baseline, after completing the intervention, and before the mock MRI. The Short STAI is a 6-item, adapted version of the well-validated Spielberger State-Trait Anxiety Inventory Scale.³⁵ It distinguishes between general proneness to anxious behavior rooted in the personality and anxiety connected to a current state, and has been validated for use in children.³⁵

Demographics and Relevant History

Demographic and possible confounding information (age, sex, prior experience with medical imaging, experience with virtual reality, type of mobile phone) will be obtained through a data collection form. Data will be de-identified using a participant identification number.

Length of Stay (LoS)

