A priori power analysis was calculated using G-Power.³⁸ A total sample size (N) of 93 was calculated to be needed across the 3 groups (31 per group), with a significance level of 95% ($\alpha=0.05$) and a power of 90% ($\beta=0.10$), allowing for a 10% drop out rate. An effect size of 0.2 was selected to reflect the research suggesting that CLS preparation can reduce sedation rates by 20%.

Descriptive analysis will be conducted on the demographics and relevant history data.

Differences in predictive success of the MRI simulation ranking scores (pass or fail) will be examined using a Repeated Measures ANOVA, within-between interaction for three timepoint measurements (before, during, after) of anxiety and delivery type (VR, mock MRI, booklet). In the case of an off-normal distribution, non-parametric tests may be used. Multivariate analysis will test for possible confounding effects (demographics and relevant history).

Survey data (USE questionnaire, Smileyometer) will be analyzed using means and standard deviations of all respondents for each category of the questionnaires. The proportions of the participants reporting high, medium, or low levels will also be calculated.

Study staff will document responses to the guided survey and read the recorded answers back to participants to verify accuracy and elicit possible further reflection. All of the qualitative data will be uploaded to NVivo by study staff. When complete, study staff will code the information to identify major themes, gaps, barriers within the existing approach and the team will devise recommendations for improving the preparation programs. The phases of this process include:

- Familiarizing yourself with the data

- Generating initial codes
- Searching for themes
- Reviewing themes
- Defining and naming the themes
- Triangulation with other findings and producing a report

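### The pass/fail primary outcome has no usable model, and the child's pre-test anxiety score, already collected, is not among the planned covariates

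*Combined protocol and SAP*

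**What the plan says.** All references are to section 4.4 of the combined protocol and SAP unless stated otherwise.

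- **Outcome.** "The primary outcome variable is likelihood of success (pass/fail) of the MRI simulation, and will be measured at the end of the assessment". The rule is objective: "The fail threshold is set at 3mm of movement in any of the positional displacements (x,y,z"). Each child contributes one binary result.
- **Analysis.** Under Analysis and Interpretation: "Differences in predictive success of the MRI simulation ranking scores (pass or fail) will be examined using a Repeated Measures ANOVA", with a "within-between interaction for three timepoint measurements (before, during, after) of anxiety and delivery type".
- **Covariates.** "Multivariate analysis will test for possible confounding effects (demographics and relevant history"). Under Demographics and Relevant History these are age, sex, earlier imaging, VR experience and type of phone. No anxiety score is listed.
- **Timing of child anxiety (Implementation Plan).** At step 3, "Participants will complete the Venham Picture Test (VPT) with staff (pre-test"). The arm is revealed at step 4 and preparation is step 7. At step 10, after preparation, "Upon entering the simulation room, participants will verbally complete the VPT with staff (during test"). The third reading, step 12, follows the simulated scan.
- **Rationale.** Section 3.0 says that "anxiety can cause non-compliance or unintentional movement which often leads to failure to complete the procedure or poor image quality".

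**The concern.** Two gaps meet in one sentence of the analysis plan.

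First, a within-between repeated measures ANOVA needs a response measured several times. Anxiety is measured three times and pass/fail once. The sentence therefore specifies an analysis of anxiety and leaves the primary outcome without a model.

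Second, pass/fail has no baseline value of its own. The nearest substitute is the step 3 Venham score, because the plan's own rationale links anxiety to movement and movement decides the result. The score costs nothing extra, yet it is not a named covariate, while phone type is.

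What is at stake is some precision, protection against chance imbalance between small groups, and protection against covariates being chosen after the data are seen. Imbalance matters a little more here than usual, because children are randomised only among the options available on the days they can attend.

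**Working it through.** **1. The plan's own figure.** The stated sample size is 93 (31 per group) for alpha 0.05, 90% power, effect size 0.2 and 10% dropout. For the within-between interaction with 3 groups and 3 readings, the noncentrality is f² × N × 3 / (1 − ρ), with 4 and 2(N − 3) degrees of freedom. With f = 0.2 and an assumed ρ = 0.5 between readings, N is 67, or 69 in equal groups, and 69/0.9 = 76.7, so 77 after dropout. A total of 93 after dropout needs ρ of about 0.37 to 0.38. Neither ρ nor the effect-size metric is stated, so 93 is neither reproduced nor shown to be wrong. The calculation does not bear on pass/fail.

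**2. Unadjusted power for pass/fail.** Inputs:
- Pass rate 82%, borrowed from section 3.0 (283/344 = 0.823 converted to non-sedated MRI after simulation).
- Comparator 62%, an assumption: 20 points lower, matching the 20% reduction cited in the sample-size paragraph.
- n = 31 per arm, two-sided 5% (also an assumption, as sidedness is not stated).

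Unpooled variance: 0.82 × 0.18 + 0.62 × 0.38 = 0.1476 + 0.2356 = 0.3832. SE = √(0.3832/31) = 0.1112. Power = Φ(0.20/0.1112 − 1.96) = Φ(−0.161) = 43.6%. With the pooled variance under the null, power is 41.6%. With 28 per arm (31 less 10% dropout) the pooled figure is 38.2%. On the pooled formula, 90% power needs 104 per arm.

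**3. Adding the pre-test score.** If r is the correlation of the pre-test score with pass/fail, the variance is multiplied by about (1 − r²). The documents give no r, so a range is shown.

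| r | 1 − r² | SE (unpooled) | Power, unpooled | Power, pooled | Gain (points) |
|---|---|---|---|---|---|
| 0 | 1.00 | 0.1112 | 43.6% | 41.6% | – |
| 0.1 | 0.99 | 0.1106 | 44.0% | 42.0% | 0.4 |
| 0.2 | 0.96 | 0.1089 | 45.1% | 43.1% | 1.5 |
| 0.3 | 0.91 | 0.1061 | 47.0% | 45.0% | 3.4 |
| 0.4 | 0.84 | 0.1019 | 50.1% | 48.1% | 6.5 |
| 0.5 | 0.75 | 0.0963 | 54.7% | 52.7% | 11 |

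These gains are against a model with no covariates. The plan already intends to use age, sex and imaging history, so the relevant r is the partial correlation given those, which is probably smaller.

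**4. Check by simulation.** Logistic models, 1,500 trials per setting, with the correlation placed on the underlying liability: power went from 42.6% to 45.4% at 0.3, from 44.1% to 50.7% at 0.5 and from 43.6% to 52.1% at 0.6. The gain is of the same order, and smaller at 0.5. In a separate simulation the relative efficiency of the adjusted risk difference was 0.99 when baseline anxiety had no effect, and 1.02, 1.14 and 1.32 for logistic slopes of 0.5, 1.0 and 1.5 per SD. An uninformative score therefore costs almost nothing.

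**5. Chance imbalance.** Under full randomisation, the difference between two arms in a standardised baseline score has standard error √(2/31) = 0.25 SD.

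**6. Room for covariates.** With two arms at 82% and one at 62%, expected failures are 31 × (0.18 + 0.18 + 0.38) = 22.9, consistent with a range of about 20 to 25.

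**The case against.** *The sentence may simply describe the anxiety analysis.* The Venham test is listed among the primary measures, so the two outcomes may have been merged in drafting. That is plausible, but pass/fail is then left with no model at all. The fallback to non-parametric tests and the multivariate step do not fill the gap, because neither names a test or model for pass/fail.

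*A reader might infer that the plan adjusts pass/fail for anxiety measured after preparation, and so removes part of the effect it seeks.* The documents do not support this. In a within-between ANOVA the anxiety readings are the response and nothing is conditioned on them. Removal would follow only if an analyst entered the step 10 or step 12 reading as a predictor, which the text does not say. On that reading the pre-test score would already be in the model too. No share of the effect acting through anxiety is given, so no size can be put on it. What stands is that the wording is loose enough to justify one sentence ruling it out.

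*The prognostic link is weak.* Section 3.0 says that anxiety can cause movement during imaging. It does not say that an eight-card score taken earlier predicts a mock scan, and recruitment is open to children with no MRI scheduled. This stands: the score is plausibly prognostic, not shown to be so.

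*The pre-test may not be clean in every arm.* Children enter the intervention room at step 1, and the comparison-groups table places the mock MRI arm in the Simulation Room. The documents do not say where that arm completes step 3. If it is there, the score may follow sight of the simulator in one arm only, and adjusting for it could introduce bias. This also stands, and the fix has to deal with it.

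**Conclusion.** The point holds in a limited form. The plan gives no usable model for its single binary primary outcome, and its covariate list omits a baseline anxiety score that is already collected. Both follow from the text without any assumption.

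The size of the benefit does rest on assumptions: 62% against 82%, 31 per arm and an unknown correlation. It is negligible at a correlation of 0.1, about 3 points of power at 0.3 and about 11 points at 0.5, less whatever the planned covariates already explain. Adjustment does not bring pass/fail near 90% power. The stronger argument is prespecification: a stated model, with protection against imbalance under allocation limited by availability. This is a worthwhile correction to the wording, not a flaw that invalidates the trial.

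**What to change.** In Analysis and Interpretation:

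1. Analyse pass/fail with one prespecified model, for example logistic regression reported as a standardised risk difference with 95% CI. Include delivery mode, the step 3 Venham score and a short fixed set of the covariates already planned, such as age.
2. Analyse the three anxiety readings separately, as their own outcome.
3. State that the step 10 and step 12 readings are not covariates for pass/fail, because both follow preparation and the second also follows the test.
4. In the Implementation Plan, confirm that step 3 is completed before any sight of the simulator in every arm, including mock MRI.

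Items 1 to 3 change wording only and need no new data. Item 4 may need a change of room or order for the mock MRI arm if its pre-test is now taken in the Simulation Room. The statistical cost is one extra parameter against roughly 20 to 25 expected failures, which is why the rest of the covariate list should be short.

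### The anxiety analysis may be replaced by unnamed non-parametric tests on an undefined trigger; one baseline-adjusted arm comparison, used whatever the distribution, would close the gap and had more power in simulation

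*Combined protocol and SAP*

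**What the plan says.** Under Analysis and Interpretation in section 4.4, the between-arm analysis is one sentence. It opens "Differences in predictive success of the MRI simulation ranking scores (pass or fail) will be examined using a Repeated Measures ANOVA" and goes on to a "within-between interaction for three timepoint measurements (before, during, after) of anxiety and delivery type (VR, mock MRI, booklet"). The next sentence is the fallback: "In the case of an off-normal distribution, non-parametric tests may be used". The section does not say how departure from normality is judged, whether raw scores or residuals are examined, which variable is meant, which test would replace the ANOVA, or whether that test must still address time-by-arm. A further sentence plans multivariate analysis of demographics and relevant history as possible confounders; the pre-test anxiety score is not named there.

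The Venham Picture Test (VPT) "comprises eight cards which two figures on each card, one anxious character and one non-anxious character". On scoring: "If the child points at the anxious figure, a score of one is recorded", and zero otherwise. The total therefore runs from 0 to 8; the summing is implied and not stated. The VPT is listed as primary in the outcome table and under Primary Measures. The parental Short STAI is primary in that table but sits under Secondary Measures in the text. Earlier in section 4.4, pass/fail of the simulation is called the primary outcome variable.

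**The concern.** A bounded count with nine possible values will not look normal, so the person analysing the data is likely to face this choice. Since nothing is fixed, the test on a primary measure can be picked with the results in view, and different picks answer different questions. Two tests that are commonly reached for are Friedman within each arm and Kruskal-Wallis at each reading. The first looks at change over time and does not compare arms. The second compares arms at one reading and reacts to a difference that was already there at baseline. The particular risk is a conclusion that VR worked and the booklet did not, drawn from one significant and one non-significant within-arm test. That would be a poor answer to hypothesis 2a.

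**Working it through.** **Inputs from section 4.4.** Three arms and three readings; "An effect size of 0.2 was selected"; alpha 0.05; power 90%; 93 children, 31 per arm, "allowing for a 10% drop out rate". Evaluable per arm: 31 × 0.9 = 27.9, taken as 28 (84 in all).

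**The plan's own figure.** The fallback has none. The nearest is N = 93. Reading 0.2 as Cohen's f for the interaction, λ = f²·N·m·ε/(1−ρ) with df (k−1)(m−1)ε and (N−k)(m−1)ε. With ρ = 0.5 and ε = 1 (assumed, not stated), N = 67 gives λ = 0.04 × 67 × 3 / 0.5 = 16.1 on 4 and 128 df, and power just over 90%. Equal arms need 69, and 69/0.9 = 76.7, so 77. A value of ρ near 0.38 gives 83, and 83/0.9 = 92.2, so 93. As ρ and ε are not given, 93 cannot be verified, but it is not shown to be too small for the interaction test. That is separate from this point.

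**Assumed score model.** The documents give no VPT distribution. Scores were simulated as binomial(8, p) with logit(p) varying normally between children, over a range of baseline means, with 28 or 31 per arm. The Short STAI was not simulated.

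**Step 1: would a normality check fail?** Shapiro-Wilk at 0.05:

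| What is checked | Trials rejecting |
|---|---|
| Raw scores, any baseline mean tried | 99-100% |
| ANOVA residuals, mean about 2 to 4.5 | 5-34% |
| ANOVA residuals, mean about 1 (heavy floor) | 96-99% |

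The unstated choice between raw scores and residuals can decide which analysis is run.

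**Step 2: what would the replacement test?**

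- Friedman, arms pooled, with a common time effect and no arm difference: rejects in 95-100% of trials.
- Kruskal-Wallis at each reading (Bonferroni), with a constant arm difference and no interaction: rejects in 41-49%.
- Kruskal-Wallis on change scores, and the rank-based factorial (ANOVA-type) statistic: about 5% with no interaction, so both are valid for time-by-arm.

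**Step 3: is a switch needed to protect type I error?** With no interaction the planned ANOVA rejected in 4.4-5.5% of trials. A comparison of the post-preparation score adjusted for the pre-test score rejected in 4.0-5.5% under its null. In these settings there was no excess to correct.

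**Step 4: power.** The adjusted analysis is Y(step 10) = a + b·Y(step 3) + arm, tested with an F on 2 and 84 − 4 = 80 df. Set B uses latent SD 1.4, correlation 0.75 and a logit shift of 0.8 at step 10, placed in the VR and mock MRI arms; placing it in VR alone gave the same pattern.

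| Setting, 28 per arm | Planned ANOVA | Kruskal-Wallis | Baseline-adjusted |
|---|---|---|---|
| Set A, baseline mean about 1.3 | 35-38% | 34-36% | 45-47% |
| Set B, mean 1.2 | 21% | 22% (change), 27% (step 10) | 37% |
| Set B, mean 1.9 | 33% | 30% (change), 33% (step 10) | 47% |
| Set B, mean 0.6 | 14% | 14% (change), 22% (step 10) | 25% |

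Gain of baseline adjustment over the planned ANOVA: 45 − 38 = 7 to 47 − 35 = 12 points in set A; 37 − 21 = 16, 47 − 33 = 14 and 25 − 14 = 11 points in set B.

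In a further set of runs without the adjusted analysis, rank tests of differing change (change-score Kruskal-Wallis with Bonferroni, and the factorial statistic) ranged from about 21 points below the planned ANOVA to about 1 point above. Kruskal-Wallis on a single reading sometimes exceeded the ANOVA (22% against 14% in the last row above), but it tests a different hypothesis.

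**The case against.** The fair defence is that the text says tests may be used, that no normality test is planned, and that this is a conventional reservation. Part of that stands: the switch is an option, and its likelihood depends on a check and a score distribution that the documents do not give. But an open option is what lets the data choose the test.

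A reader might infer more than the documents support:

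- *That rank tests cannot address the planned question.* Some can (step 2), and the plan excludes none of them.
- *That the fallback drops baseline adjustment.* The planned ANOVA treats the pre-test as one of three readings. It has no baseline covariate to lose.
- *That the switch is near certain.* This holds for a formal check of raw scores, and not for a residual check without a heavy floor.
- *That the fallback causes the power gap.* In sets A and B, Kruskal-Wallis was at most a few points below the planned ANOVA and sometimes above it. The gap is what baseline adjustment gains.
- *That within-arm tests will mislead at a fixed rate.* Two independent tests disagree with probability 2p(1−p), which peaks at 50% when p = 0.5. Separate Friedman tests in VR and booklet, with no arm difference, disagreed in 13% of trials at a common time effect of 0.2 on the logit scale, 49% at 0.8, 18% at 1.2 and 1% at 1.6. The plan does not propose such tests.

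It is also fair to say that hypothesis 2a is about arm differences and does not mention time, so a rank comparison of arms after preparation would bear on it. The same is true of the adjusted contrast recommended here. Finally, the sentence before the fallback names pass/fail as its outcome, a binary variable that cannot be normal. That is a more basic defect, but a separate one.

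**Conclusion.** The point holds as a weakness in the choice of analysis, of moderate weight. An undefined trigger and an unnamed replacement leave the test, and possibly the hypothesis, for a primary measure open until the data are seen. The switch buys no protection of type I error in the settings examined, and a better single analysis is available from a pre-test score that the trial already collects. The gain was 7 to 16 percentage points of power over the planned ANOVA.

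These figures rest on assumed VPT distributions and on an effect present at the step 10 reading. They rank the methods; they do not estimate the power of this trial, and a reader should not take 35-38% as evidence that it is underpowered. The case for fixing the analysis in advance needs no simulation.

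**What to change.** Delete the fallback sentence. State one analysis for the VPT and the Short STAI, used whatever the distribution: arm contrasts (VR versus booklet, VR versus mock MRI) on the post-preparation score taken on entering the simulation room (step 10), adjusted for the pre-test score (step 3), with 95% confidence intervals. For hypothesis 2b the interval should be reported, since a non-significant result does not show equality. The Short STAI paragraph times its readings differently from the implementation steps (baseline, after the intervention, before the mock MRI), so the two should be reconciled to identify the reading used.

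A permutation p-value or a bootstrap interval may be added as a sensitivity check. The permutation must follow the allocation rule in section 4.4, redrawing each child's arm only from the options open to that child, so those options need to be on record. State that separate within-arm tests will not be used to compare arms.

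The cost is two or three sentences of text and, if the permutation check is kept, a short script. No new data from participants are needed.
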